## **12.5 Sponsor or FDA Monitoring**

The NCI, DCCPS (or their designee) may audit various aspects of the study. This auditor will be given access to facilities, databases, supplies and records to review and verify data pertinent to the study. This protocol does not include pharmaceuticals or require FDA monitoring.

## **12.6 Record Retention**

Clinical records for all participants, including CRFs, all source documentation (containing evidence to study eligibility, history and physical findings, laboratory data, results of consultations, *etc.*), as well as IRB records and other regulatory documentation will be retained by the Investigator in a secure storage facility in compliance with Health Insurance Portability and Accountability Act (HIPAA), Office of Human Research Protections (OHRP), Food and Drug Administration (FDA) regulations and guidances, and NCI/DCCPS requirements, unless the standard at the site is more stringent. The records for all studies performed under an IND will be maintained, at a minimum, for two years after the approval of a New Drug Application (NDA). For NCI/DCCPS, records will be retained for at least three years after the

completion of the research. NCI will be notified prior to the planned destruction of any materials. The records should be accessible for inspection and copying by authorized persons of the Food and Drug Administration. If the study is done outside of the United States, applicable regulatory requirements for the specific country participating in the study also apply.

## **13. STATISTICAL CONSIDERATIONS**

### **13.1 Study Design/Description**

#### **13.1.1. Primary Objectives**

To determine feasibility (recruitment, accrual, retention, adherence) of a RCT of a stepped-care telehealth mental health intervention (tailored to symptom level) versus enhanced usual care in 90 post-treatment cancer survivors with moderate or severe levels of emotional distress (anxiety and/or depressive symptoms).

#### **13.1.2. Secondary Objectives**

To obtain preliminary data on the efficacy and variability of a stepped-care telehealth mental health intervention (tailored to symptom level) versus enhanced usual care for reducing emotional distress (anxiety and/or depressive symptoms) in 90 post-treatment cancer survivors.

To obtain preliminary data on the efficacy and variability of a stepped-care telehealth mental health intervention (tailored to symptom level) versus enhanced usual care for secondary outcomes (sleep disturbance, fatigue, fear of recurrence, cancer-related distress, and QOL) in 90 post-treatment cancer survivors.

To determine costs associated with both stepped-care telehealth and enhanced usual care interventions from the perspective of a healthcare provider. We will determine costs of intervention implementation and health care utilization in all arms over the course of the interventions.

#### **13.1.3. Exploratory Objectives**

To examine potential differential effects of the intervention on anxiety, depression, sleep disturbance, fatigue, fear of recurrence, and QOL, by gender, age, race/ethnicity, stratification arm (moderate, severe), and psychotropic medication use at baseline.

To examine mediating effects of expectancy ratings of the intervention on anxiety and depression.

### **13.2 Randomization/Stratification**

Participants will be stratified by baseline score  $\geq 15$  on the GAD-7 and/or on the PHQ-9, indicating severe anxiety or depressive symptoms, and by whether they qualified for the study by the GAD-7, PHQ-9, or both. Participants with moderate symptoms only (8-14 on the PHQ-9 and  $< 15$  on the GAD-7 or 10-14 on the GAD-7 and  $< 15$  on the PHQ-9) will be randomized to either the low-intensity stepped-care telehealth or to the enhanced usual care (EUC control) with equal probability. Participants with severe symptoms will be randomized to either the high-intensity stepped-care telehealth intervention or the EUC control with equal probability. Participants randomized to the low-intensity stepped care telehealth arm who experience increased symptoms at week seven and now experience severe level of symptomatology will receive the high-intensity intervention (see Section 7.1). Analysis will proceed as intent-to-treat using

their initial stepped-care telehealth assignment; we do not anticipate that many people will change from moderate to severe during the study. We anticipate enrolling 45 patients in the stepped-care telehealth intervention and 45 in the enhanced usual care group. We will enroll 50 participants in the moderate symptom strata, and 40 participants in the severe symptom strata. Block sizes will be chosen randomly to ensure that future assignments cannot be inferred from previous ones.

### 13.3 Sample Size

The sample size (N=90) is based on goals of estimating retention, recruitment, adherence and accrual rates and effect sizes to inform design of a larger efficacy trial. If the drop-out rate is  $>30\%$ , a larger study may not be feasible. With N=90, we are confident that this rate will be  $\leq 30\%$  when the observed drop-out rate is as large as 22% (upper limit of the one-sided 95% CI is 29.2%). Similarly, the lower limit of a one-sided 95% confidence interval for the recruitment rate can be estimated within 8.2% of the observed rate if we approach at least 100 participants to recruit 90, and the lower limit of a one-sided 95% confidence interval for the adherence can be estimated within 8.7% of the observed rate with N=90. Using the normal approximation to the Poisson, we can estimate the lower limit of the one-sided 95% confidence interval of the accrual rate within approximately 2 people per month if the observed rate is 11 people per month. To compare differences between the groups on changes in the PHQ-9 and GAD-7 scores, we can estimate the intervention effect within  $\pm 0.46$  SD with a sample size of 36/group (stepped-care telehealth, enhanced usual care), allowing 20% dropout of the 45/group randomized. This corresponds to 2.7 points on PHQ-9 and 1.9 points on GAD-7 using SDs from studies of change in the measures of 5.8 and 4.2 points, respectively.

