### **5.2 Adherence**

Adherence will be recorded as the percentage of therapy sessions (for the high-intensity intervention group) or check-in calls (for the low-intensity intervention group) each participant completes.

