## 8. CRITERIA FOR EVALUATION AND ENDPOINT DEFINITION

### 8.1 Primary Endpoint

To determine study feasibility, recruitment, accrual, retention, and adherence rates will be calculated as follows:

**Recruitment.** To determine recruitment rate, we will track number of individuals who met all eligibility criteria and percent who agree to participate.

**Accrual.** Accrual rates will be calculated by calculating the mean number of participants recruited per month.

**Retention.** Study retention will be estimated by the proportion of participants who complete the Week 13 visit. Drop-out is defined as 100% minus the dropout %.

**Adherence.** Intervention adherence will be estimated as the mean percentage of therapy (high-intensity intervention) or check-in (low-intensity intervention) sessions each participant completes.

The Working Alliance Inventory will be summarized with descriptive statistics to describe the therapist-participant relationship as a process measure

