### **13.7 Reporting and Exclusions**

Unless we receive written or verbal withdrawal of consent, we will try to reach every participant for telephone calls, telephone sessions, and assessments as outlined in the protocol.

The dataset used in the analysis of Objective 1.1.1 will include all eligible participants to calculate recruitment rates. Accrual, retention, and adherence will be calculated on the participants who consent to participate in the study. The analysis of the secondary objectives and exploratory objective will include all participants who consent to participate in the study. The ANOVA models used for the secondary objectives use data from all available time points and allows for data to be missing at random. For the analyses of the secondary objectives and the exploratory objective, we will use an intent-to-treat approach. If participants are moved from low intensity to high intensity they will be analyzed using the

low intensity assignment (intent to treat). In exploratory models, we will analyze the impact of adherence by including it as a predictor.

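### The adherence precision of 8.7% in Section 13.3 is computed on all 90 participants, but only about 45 can have an adherence value; the same formula then gives 12.3%.

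*Combined protocol and SAP*

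**What the plan says.** Section 13.3 (Sample Size) supports N = 90 partly through the precision of the feasibility estimates. For adherence it says that "the lower limit of a one-sided 95% confidence interval for the adherence can be estimated within 8.7% of the observed rate with N=90".

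Section 5.2 defines adherence as the "percentage of therapy sessions (for the high-intensity intervention group) or check-in calls (for the low-intensity intervention group) each participant completes". Section 8.1 makes it a primary endpoint: "Intervention adherence will be estimated as the mean percentage of therapy (high-intensity intervention) or check-in (low-intensity intervention) sessions each participant completes".

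Section 13.2 gives the allocation: "We anticipate enrolling 45 patients in the stepped-care telehealth intervention and 45 in the enhanced usual care group". It also plans 50 participants in the moderate stratum and 40 in the severe stratum, each randomised with equal probability to stepped care or EUC.

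Section 13.7 sets the analysis dataset: "Accrual, retention, and adherence will be calculated on the participants who consent to participate in the study".

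The EUC description in Section 7.1 lists referral information, self-help resources and a booklet. The Study Parameter Table (Section 7.9) assigns check-in calls to the low-intensity arm and weekly therapist activities to the high-intensity arm.

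**The concern.** Adherence exists only for people who have sessions or calls to attend. By design that is half of the randomised sample, yet the stated precision uses the whole of it. Section 13.7 does not correct this, because it takes everyone who consents as the adherence dataset.

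Adherence is one of the four components of the single primary objective, and Section 13.3 names it among the grounds for N = 90. Section 13.4 then uses confidence limits to judge whether further work is feasible. If the precision is overstated, readers will expect a tighter adherence limit than the design guarantees, and the larger trial would be planned on that expectation. If EUC participants were literally counted in the denominator, their values would be undefined. If they were scored as zero, perfect adherence in stepped care would average (45 × 100 + 45 × 0)/90 = 50%.

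**Working it through.** **Inputs**

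- One-sided 95% confidence, z = 1.645; stated margin 8.7% with N = 90 (Section 13.3).
- Companion figures in the same section: a recruitment margin of 8.2% with 100 approached, and a drop-out upper limit of 29.2% at an observed 22%, n = 90.
- 45 participants in stepped care and 45 in EUC (Section 13.2).
- Strata of 50 and 40, equal allocation (Section 13.2): 50/2 = 25 low-intensity and 40/2 = 20 high-intensity participants.
- Adherence defined for stepped care only (Sections 5.2 and 8.1).

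**Step 1: reproduce the plan's figure**

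Formula: margin = z × √(p(1 − p)/n), with p = 0.5 as the worst case.

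- Adherence, n = 90: 1.645 × √(0.25/90) = 8.67 points (stated 8.7).
- Recruitment, n = 100: 1.645 × √(0.25/100) = 8.22 points (stated 8.2).
- Drop-out, p = 0.22, n = 90: 0.22 + 1.645 × √(0.22 × 0.78/90) = 29.18% (stated 29.2%).

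Other forms for adherence at n = 90 and p = 0.5 do not match: two-sided 10.33, continuity-corrected 9.22, exact Clopper-Pearson 9.12, t quantile with an SD of 50 points 8.76. The plain one-sided Wald form fits all three stated figures, so the 8.7% does rest on 90 adherence values.

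**Step 2: use the participants who can have an adherence value**

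| Group | n | Worst-case margin (points) |
|---|---|---|
| As stated | 90 | 8.67 |
| Stepped care | 45 | 1.645 × √(0.25/45) = 12.26 |
| Low intensity | 25 | 1.645 × √(0.25/25) = 16.4 |
| High intensity | 20 | 1.645 × √(0.25/20) = 18.4 |

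The ratio of the second row to the first is √(90/45) = √2, whatever fixed p or SD is used.

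**Step 3: allow for the endpoint being a mean percentage**

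The documents give no SD for percent of sessions completed, so these SDs are assumptions. Formula: margin = 1.645 × SD/√n.

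| Assumed SD (points) | n = 45 | n = 90 |
|---|---|---|
| 20 | 4.9 | 3.5 |
| 25 | 6.1 | 4.3 |
| 30 | 7.4 | 5.2 |
| 40 | 9.8 | 6.9 |
| 50 (same as p = 0.5) | 12.3 | 8.7 |

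The SD at which 45 participants give exactly the stated margin is 8.67 × √45/1.645 ≈ 35 points.

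**The case against.** The strongest reply is that 12.3 points need not be the precision the trial achieves. It is the bound for a yes/no outcome at 50%. For a mean of percentages it corresponds to an SD of 50 points, reached only if half the participants complete everything and half complete nothing. With an SD of about 35 points or less, 45 participants would still give a margin within 8.7 points. Treated as a proportion, adherence of about 85.4% or more would do so too. This stands: what is lost is the worst-case guarantee, and achieved precision may be better. It does not rescue the stated figure, which uses the same worst-case convention and the wrong n. Since a 0–100 variable has an SD of at most about 50 points, 12.3 is a valid bound at n = 45.

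Second, Section 13.7 can be read kindly: EUC participants have no adherence value, so they drop out of the mean. A sensible analyst would probably do this. The change there is a clarification, but the denominator of a primary measure should be written down.

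Third, no adherence threshold is stated, and the only numerical feasibility limit in Section 13.3 is drop-out above 30%, which correctly uses all 90. That is true and limits the consequence.

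Finally, Section 12.4 mentions check-in calls for the EUC group when describing how adverse events are elicited. Neither the EUC description nor the Study Parameter Table provides such calls, and the adherence definition excludes EUC, so N = 90 is not supported by this.

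**Conclusion.** The concern holds. The arithmetic behind 8.7% is correct for 90 observations, but the design supplies about 45. On the plan's own formula the margin is 12.3 percentage points, about 3.6 points (12.26 − 8.67) or √2 times wider than stated. This rests on the planned 45/45 allocation and on the worst-case convention that Section 13.3 itself uses. The achieved margin depends on an SD that the documents do not give.

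The stated precision of a primary feasibility measure is wrong as written and should be corrected. No stated go/no-go rule changes, and the by-intensity margins matter only if adherence is reported separately by intensity.

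**What to change.** - **Section 13.3:** replace the adherence figure with a worst-case margin of 12.3 percentage points with N = 45 randomised to stepped care. If adherence will be reported by intensity, add 16.4 points (low, n = 25) and 18.4 points (high, n = 20). Labelling these as worst case, or adding a margin under a stated SD assumption, would fit the mean-percentage endpoint better.
- **Section 13.7:** restrict the adherence dataset to participants randomised to stepped care.
- **Section 12.4:** reconcile the mention of EUC check-in calls with Section 7.1 and the Study Parameter Table.

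The main correction costs two sentences and a less favourable precision statement. Sample size, conduct and data collection are unchanged.

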### 13.4 Primary Objective, Endpoint(s), Analysis Plan

For Objective 1.1.1, recruitment, accrual, retention, and adherence rates will be calculated. To determine the recruitment rate, we will track number of eligible participants and percent who agree to participate. Accrual rates will be calculated by calculating the mean number of participants recruited per month. Study retention will be estimated by the proportion of participants who complete the Week 7 and 13 visits. Intervention adherence will be estimated as the mean percentage of therapy or check-in sessions each participant completes. Drop-out is defined as 100% minus the dropout %. 95% confidence intervals will be calculated for each measure to quantify uncertainty in the estimates and to determine if the lower (recruitment, accrual) or upper (retention, adherence) limit would indicate lack of feasibility for future work.

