## **5. INTERVENTION PARAMETERS (RETENTION, ADHERENCE, TREATMENT FIDELITY)**

### **5.1 Study retention**

Study retention will be estimated by the proportion of participants who complete the Week 7 and 13 visits.

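### Section 13.4 judges retention and adherence by the upper confidence limit, where the lower one is needed, and so contradicts section 13.3

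*Combined protocol and SAP*

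**What the plan says.** Feasibility is the only primary objective. Section 13.4 states that "95% confidence intervals will be calculated for each measure to quantify uncertainty in the estimates" and then gives their use: "to determine if the lower (recruitment, accrual) or upper (retention, adherence) limit would indicate lack of feasibility for future work". It does not say whether the intervals are one-sided or two-sided.

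In the same section retention is the share of participants completing visits, and adherence is the average share of therapy sessions or check-in calls completed per participant.

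Section 13.3 holds the plan's only numeric feasibility criterion. If drop-out exceeds 30%, "a larger study may not be feasible". The authors are satisfied on this point "when the observed drop-out rate is as large as 22% (upper limit of the one-sided 95% CI is 29.2"%). For adherence, 13.3 states that "the lower limit of a one-sided 95% confidence interval for the adherence can be estimated within 8.7% of the observed rate with N=90". Recruitment and accrual also get lower one-sided limits there.

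The sentence that should connect retention and drop-out, in both 8.1 and 13.4, reads "Drop-out is defined as 100% minus the dropout" percentage.

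Retention has two definitions. Section 8.1 says "Study retention will be estimated by the proportion of participants who complete the Week 13 visit"; section 5.1, like 13.4, says "Study retention will be estimated by the proportion of participants who complete the Week 7 and 13 visits".

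**The concern.** All four feasibility measures run in the same direction: more recruitment, accrual, retention and adherence is better. The cautious limit is the lower one for each. Section 13.4 follows this for recruitment and accrual but reverses it for retention and adherence.

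An upper limit on retention falls below a minimum standard only when the result is very poor. A rule that waits for this lets through results that section 13.3 would count against a larger trial. Because the study exists to inform that larger trial, two sections that support opposite conclusions from the same data are a real defect in the primary analysis plan.

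**Working it through.** **Inputs.** From 13.3: N = 90, a drop-out mark of 30% (retention 70%) and one-sided 95% limits. From 13.4: the limit named for each measure. z = 1.645 one-sided, 1.96 two-sided.

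**1. Reproduce section 13.3.** Wald limit: p ± z·√(p(1−p)/n).
- Drop-out at 22%: 0.22 + 1.645·√(0.22·0.78/90) = 0.2918, stated as 29.2%. The two-sided value would be 0.22 + 1.96·√(0.22·0.78/90) = 0.306, so 13.3 is one-sided.
- Adherence margin, assuming p = 0.5: 1.645·√(0.25/90) = 0.0867, stated as 8.7%.
- Recruitment margin, assuming p = 0.5 and 100 approached: 1.645·√(0.25/100) = 0.0822, stated as 8.2%.
- Accrual of 11 per month over 90/11 months: 1.645·√(11/(90/11)) = 1.91, stated as about 2.

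The margins show only that z = 1.645 was used. The direction comes from the text of 13.3, which names the limit for each measure.

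**2. Compare the directions.**

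| Measure | 13.3 | 13.4 |
|---|---|---|
| Recruitment | lower | lower |
| Accrual | lower | lower |
| Adherence | lower | upper |
| Retention | lower (as the upper limit for drop-out) | upper |

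The complement is exact: retention of 78% has a one-sided lower limit of 70.8% = 100% − 29.2%. Its upper limit is 85.2%.

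**3. Cut-offs for retention.**
- Rule of 13.3: the upper limit for drop-out must not exceed 30%. With 20/90 the limit is 0.294; with 21/90 it is 0.307. At most 20 drop-outs (22.2%) pass.
- Literal 13.4: flag only if the upper limit for retention is below 70%. With 56/90 retained the limit is 0.706; with 55/90 it is 0.696. Up to 34 drop-outs (37.8%) go unflagged.
- The sections disagree for any result from 21 to 34 drop-outs.

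**4. Chance of no infeasibility flag.** X ~ Binomial(90, true drop-out), one-sided limits.

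| True drop-out | 13.3: P(X ≤ 20) | Literal 13.4: P(X ≤ 34) |
|---|---|---|
| 30% | 6.5% | 95.5% |
| 35% | 0.6% | 74.8% |
| 40% | 0.03% | 37.6% |
| 45% | <0.01% | 10.1% |

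**5. Sensitivity to the interval.** With two-sided 95% Wald limits the cut-offs are 19 and 36, giving 3.9% against 98.4% at a true drop-out of 30%, and 0.01% against 54.6% at 40%. With exact (Clopper-Pearson) one-sided limits they are 19 and 34. The gap does not come from the choice of formula.

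**The case against.** The strongest objection is that step 4 describes a hybrid rule. Section 13.4 has no threshold, and the 30% mark in 13.3 sits beside the correct limit, so an analyst who takes the number would probably take the direction with it. Neither section is a binding go/no-go rule, failing to show infeasibility is not a declaration of feasibility, and the report would show the drop-out rate with its interval. All of this stands. It makes the size conditional, but it does not make the wording of 13.4 right.

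Two readings might rescue the sentence:
- *Retention* may be a slip for *drop-out*. This is plausible and would settle retention, but adherence would still be upper in 13.4 and lower in 13.3.
- An upper limit below the standard would be firm evidence of infeasibility. That is coherent alone, but recruitment and accrual would then need the upper limit too, and 13.3 asks for confidence that drop-out is at most 30%.

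Two technical points also stand. Adherence is a mean percentage, so the binomial margin is only a worst-case approximation. It also exists only for stepped-care participants, about 45; with n = 45 the margin is 1.645·√(0.25/45) = 12.3%, not 8.7%. Neither affects the direction of the limit.

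**Conclusion.** The concern holds. Section 13.4 names the wrong limit for retention and adherence. The conflict with 13.3 is direct for adherence and follows by complement for retention; the circular drop-out sentence does not resolve it.

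The size is known for retention only. It assumes that 13.4 is applied literally with the 30% mark from 13.3 and N = 90. On one-sided Wald limits, the tolerated drop-out then rises from 20 to 34 of 90. The effect is greatest at true drop-out of about 30% to 40%; at 45% the literal rule still flags infeasibility about 90% of the time. For adherence no error rate can be calculated without a threshold.

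No data are lost, so this is a point to correct before analysis rather than a threat to the trial. The unstated sidedness and the two retention definitions are secondary; they did not cause the error.

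**What to change.** - In 13.4, write: *Lack of feasibility will be judged by the lower limit of the one-sided 95% CI for recruitment, accrual, retention and adherence (equivalently, the upper limit for drop-out, compared with 30% as in Section 13.3).*
- In 8.1 and 13.4, replace the circular sentence with: *Drop-out % = 100% minus retention %.*
- Reconcile the retention definition across 5.1, 8.1 and 13.4 (Week 13 alone, or Weeks 7 and 13), and state which one the 30% mark applies to.
- Since only drop-out has a threshold, either give one for recruitment, accrual and adherence or say that their limits will be interpreted descriptively.

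The cost is a few sentences. No new data or participants are needed, and N = 90 and the 29.2% drop-out figure stay as they are.
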